If a patient misses any doses of AZD9291 during the 21-day evaluation period of Cycle 1, please contact the AstraZeneca Study physician or site monitor for advice regarding the evaluability of the patient and appropriate timing of the PK assessments. All other assessments, including laboratory safety assessments, vital signs and RECIST should continue to be performed as per study plan, relative to the baseline assessments.

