5.2.1 Toxicity management

If a patient experiences a CTCAE grade 3 or higher and/or unacceptable toxicity (any grade) not attributable to the disease or disease-related processes under investigation, where the Investigator considers the AE of concern to be specifically associated with AZD9291, dosing will be interrupted and supportive therapy administered as required in accordance with local practice/guidelines.

In cohort 1, if the toxicity resolves or reverts to \leq CTCAE grade 2 within 3 weeks of onset, treatment with AZD9291 may be restarted at the same dose. In cohort 2, if the toxicity resolves or reverts to \leq CTCAE grade 2 within 3 weeks of onset, treatment with AZD9291 may be restarted at the same dose (80 mg) or a lower dose (40 mg) using the rules below for dose modifications (Table 1) and with discussion and agreement with the AstraZeneca Study Team Physician as needed. There will be no individual modifications to dosing schedule in response to toxicity, only potential dose reduction or dose interruption.

If the toxicity does not resolve to \leq CTCAE grade 2 after 3 weeks, then the patient should be withdrawn from the study and observed until resolution of the toxicity.

Starting Dose	Reduced AZD9291 Dose
80 mg daily	40 mg daily
40 mg daily	no dose reduction

Table 1Dose interventions

On resolution of toxicity within 3 weeks:

• If an AE subsequently requires dose interruption, AZD9291 may restart at the same dose or the reduced dose (as per Table 1), on resolution/improvement of the AE at the discretion of the Investigator.

If new or worsening pulmonary symptoms (eg, dyspnoea) or radiological abnormality suggestive of interstitial lung disease is observed, an interruption in study treatment dosing is recommended, and the AstraZeneca study physician should be informed. A questionnaire regarding the results of the full diagnostic workup (including high-resolution computed tomography (HRCT), blood and sputum culture, haematological parameters) will be sent to Investigators. It is strongly recommended to perform a full diagnostic workup, to exclude

alternative causes such as lymphangitic carcinomatosis, infection, allergy, cardiogenic edema, or pulmonary hemorrhage. In the presence of confirmatory HRCT scans where other causes of respiratory symptoms have been excluded, a diagnosis of interstitial lung disease should be considered and study treatment permanently discontinued.

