In the absence of a diagnosis of interstitial lung disease study treatment may be restarted following consultation with the AstraZeneca Study Physician if the dosing interruption is no longer than 3 weeks.

Patients with QTcF prolongation fulfilling the following criteria (ie, confirmed QTcF prolongation to >500 msec absolute or a >60 msec increase from baseline) should have study treatment interrupted and regular ECGs performed until resolution to baseline. If the toxicity does not resolve to \leq grade 1 within 3 weeks the patient will be permanently withdrawn from study treatment.

Patients experiencing corneal ulceration or Interstitial Lung Disease (ILD) will not be permitted to restart study treatment.

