5.5 Discontinuation of investigational product and withdrawal from study

Patients **may** be discontinued from investigational product in the following situations:

- Patient decision. The patient is at any time free to withdraw his/her participation in the study, without prejudice
- Adverse events
- Pregnancy
- Severe non-compliance to this protocol as judged by the investigator and/or AstraZeneca
- Confirmed disease progression
- Patients incorrectly initiated on investigational product (Section 5.5.2)
- Patient lost to follow-up

Patients that are withdrawn from the study but are evaluable will not be replaced.

Patients may withdraw from any aspects of the voluntary exploratory research (see Section 5.5.3) at any time, without prejudice to further treatment and independent of any decision concerning participation in other aspects of the main study.

5.5.1 **Procedures for discontinuation of a patient from investigational product**

The Principal Investigator/Investigator will perform the best possible observation(s), test(s) and evaluation(s) as well as give appropriate medication and all possible measures for the safety of the subject. They will also immediately inform AstraZeneca of the withdrawal. Adverse events will be followed up; all unused study drug should be returned by the subject or representative (e.g. caretaker, family member).

If AZD9291 is discontinued for any reason, the patient must complete all assessment at discontinuation visit specified in study plan (Table 2). Study procedure related SAEs and concomitant medication must be captured till 28 day safety follow-up visit.

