5.5.3 Procedures for withdrawal from study

Patients are at any time free to withdraw from the study (investigational product and assessments), without prejudice to further treatment (withdrawal of consent). Such patients will always be asked about the reason(s) and the presence of any adverse events. If possible, they will be seen by an investigator and undergo the assessments and procedures scheduled for the post study assessment (see Section 6.4.3) and inform AstraZeneca of the withdrawal. Adverse events should be followed up (see Sections 6.4.3 and 6.4.4) and study drug should be returned by the patient.

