6.4.3 Recording of adverse events

Time period for collection of adverse events

AEs will be collected throughout the study, from informed consent until the end of the follow up period. The follow-up period is defined as 28 days after study treatment is discontinued. SAEs occurring in the follow-up period should be reported to AstraZeneca in the usual manner (see Section 6.4.4).

Following discontinuation of AZD9291, SAEs considered related to study procedures should continue to be collected while patients are followed up for disease progression, as outlined in Table 3.

	Consent to Treatment Period	Until 28-day Follow- up Visit (safety follow-up period)	Post 28-day Follow-up visit
Collect all new AEs in eCRF	Yes	Yes	No
Collect all ongoing AEs in eCRF	Yes	Yes	No
Collect all study procedure- related SAEs in eCRF	Yes	Yes	Yes
Death due to AE, or unknown cause	Yes	Yes	No

Table 3 Summary of recording and follow-up of adverse events and deaths

After the final database lock, there may be some patients remaining on study treatment. For these patients who are continuing to receive AZD9291, AZ will collect information (during the treatment period and for 28 days after last dose) on SAEs, deaths (including those due to disease progression), discontinuation due to AEs/SAEs and drug accountability only.

Follow-up of unresolved adverse events

Any AEs that are unresolved at the patient's last visit (28-day follow-up visit) in the study are followed up by the investigator for as long as medically indicated. AstraZeneca retains the right to request additional information for any patient with ongoing AE(s) at the end of the study, if judged necessary.

If an investigator learns of any SAEs, including death, at any time after a patient has completed the study and he/she considers there is a reasonable possibility that the event is related to AZD9291, the investigator should notify AstraZeneca.

Variables

The following variables will be collected for each AE:

- AE diagnosis/description
- The date when the AE started and stopped
- Changes in CTCAE grade (for skin reactions and diarrhoea only); maximum CTCAE grade for all other AEs
- Whether the AE is serious or not
- Investigator causality rating against the investigational product (yes or no)

- Action taken with regard to investigational product
- Outcome

For SAEs other variables will be collected including treatment given for the event.

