6.7 Anti-tumour activity

6.7.1 Tumour assessments

RECIST 1.1 guidelines for measurable, non-measurable, target lesions (TLs) and non-target lesions (NTLs) and the objective tumour response criteria are presented in Appendix F of this Clinical Study Protocol.

Baseline CT or MRI assessments of chest and abdomen (including liver and adrenal glands) must be performed no more than 28 days before the start of study treatment, and ideally should be performed as close as possible to the start of study treatment. Additional imaging may be performed based on individual patient signs and symptoms. CT/MRI scan of the brain should be performed in patients with known or suspected brain metastases. The methods of assessment used at baseline should be used at each subsequent follow-up assessment.

Follow-up assessment should be performed every 6 weeks (\pm 7 days) up to and including progression (corresponding with the RECIST assessments – and continuing after treatment discontinuation in the absence of disease progression).

Any other sites at which new disease is suspected should also be appropriately imaged. If an unscheduled assessment is performed and the patient has not progressed, every attempt should be made to perform subsequent assessments at the scheduled visits whilst the patient remains on study treatment.

Categorisation of objective tumour response assessment will be based on the RECIST 1.1 guidelines for response: CR (complete response), PR (partial response), SD (stable disease) and PD (progression of disease). Target lesion progression will be calculated in comparison to when the tumour burden was at a minimum (ie, smallest sum of diameters previously recorded on study). In the absence of progression, tumour response (CR, PR, SD) will be calculated in comparison to the baseline tumour measurements obtained before starting treatment.

If the investigator is in doubt as to whether progression has occurred, particularly with response to NTLs or the appearance of a new lesion, it is advisable to continue treatment and reassess the patient's status at the next scheduled assessment or sooner if clinically indicated. If repeated scans confirm progression, then the date of the initial scan should be declared as the date of progression.

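### Section 5.2.1 withdraws patients with unresolved toxicity from the study, while its own QTcF and ILD rules and 5.5 stop only treatment and 6.7.1 keeps tumour scans going

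*Protocol*

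**What the plan says.** Section 5.2.1 interrupts dosing for grade 3 or higher, or unacceptable, toxicity that the investigator attributes to AZD9291. If the toxicity has not come down to grade 2 or lower after 3 weeks, "then the patient should be withdrawn from the study and observed until resolution of the toxicity".

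Two other stopping rules in 5.2.1 are worded differently. For interstitial lung disease, "a diagnosis of interstitial lung disease should be considered and study treatment permanently discontinued". For QTcF prolongation, also with a 3-week limit, "the patient will be permanently withdrawn from study treatment".

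Section 5.5 lists when patients may be "discontinued from investigational product in the following situations", and adverse events are on that list. Section 5.5.3 describes patients as "free to withdraw from the study (investigational product and assessments), without prejudice to further treatment (withdrawal of consent").

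Section 6.7.1 sets RECIST assessments every 6 weeks (± 7 days) up to and including progression, "continuing after treatment discontinuation in the absence of disease progression". Section 6.4.3 says that after AZD9291 is stopped, procedure-related SAEs "should continue to be collected while patients are followed up for disease progression".

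**The concern.** One rule in 5.2.1 removes the patient from the study; the comparable rules remove the patient only from the drug. The protocol treats these as separate exits, with separate procedures in 5.5.1 and 5.5.3. A site that takes the general toxicity rule at its word could therefore end tumour scans that 6.7.1 requires.

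The patients concerned are selected by poor tolerability, so the lost scans would not be a random subset. They also stay in the response denominator: section 7.6 asks only for dosing and a baseline RECIST assessment, and 7.7 uses that set for tumour response. This is an instruction to sites, so an analysis plan could not recover scans that were never taken.

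**Working it through.** The plan gives no figure to reproduce. The check sets the texts side by side and then works out which onset times would matter.

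**Step 1: what each rule stops**

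| Place in protocol | Trigger | What ends |
|---|---|---|
| 5.2.1, general rule | Drug-related toxicity above grade 2 after 3 weeks | The study; observation of the toxicity continues |
| 5.2.1, QTcF rule | Not resolved to grade 1 or lower within 3 weeks | Study treatment |
| 5.2.1, ILD rule | Diagnosis of ILD | Study treatment |
| 5.5 list | Adverse events, among others | Investigational product |
| 5.5.3 | Patient withdraws consent | Product and assessments |
| 6.7.1 | Treatment discontinued without progression | RECIST does not end; it continues every 6 weeks |

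Only the first and fifth rows end study participation, and the fifth concerns the patient's own decision. The first row is the odd one out among the toxicity rules.

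**Step 2: which onset times would lose a scan under the literal reading**

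Inputs: scans at week 6k ± 1, counted from Cycle 1 Day 1 (Table 2, footnote c); withdrawal 3 weeks after onset (5.2.1). Scans continue while dosing is interrupted. Section 5.2 says so for doses missed in Cycle 1 ("vital signs and RECIST should continue to be performed as per study plan, relative to the baseline assessments"), and I assume the same for later cycles. I also assume no unscheduled scan before exit.

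- *No post-baseline scan:* onset + 3 < 6, so onset is before week 3. A first scan at week 5 gives 5 − 3 = week 2; one at week 7 gives 7 − 3 = week 4. Such a patient cannot count as a responder, but has had under about 4 weeks of daily dosing, so whether a response would have followed is unknown.
- *Response first seen at scan k, next scheduled scan lost:* 6k ≤ onset + 3 < 6k + 6, so 6k − 3 ≤ onset < 6k + 3. For k = 1 that is weeks 3 to 9, for k = 2 weeks 9 to 15, and for k = 3 weeks 15 to 21.
- *Width of each span with the scan windows:* from (6k + 5) − (6k + 1) = 4 weeks to (6k + 7) − (6k − 1) = 8 weeks; nominally 6.

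Section 7.5.1 requires repeat imaging at least 4 weeks later for a confirmed response, so the second case leaves a response unconfirmed. It changes ORR only if ORR counts confirmed responses. Section 7.5.1 defines visit and confirmed responses separately, and the synopsis, 7.1 and 7.7 do not say which one enters ORR. If visit responses count, the second case has no effect.

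**Step 3: weight of one patient**

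With about 12 patients per cohort (7.2), 1/12 = 8.3 percentage points of a cohort's ORR; over both cohorts, 1/24 = 4.2 points.

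**Step 4: what is not touched**

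When the rule applies, dosing has already been interrupted for up to 3 weeks. Any loss to the steady-state profile in Cycle 2 comes from the interruption, not from the wording. For safety, 5.2.1 keeps observation of the toxicity, 5.2.4 and 5.5.1 require the discontinuation visit whatever the reason for stopping, and 6.3.8.2 and 6.4.3 set follow-up to 28 days after the drug is stopped.

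**The case against.** The strongest reply is that this is loose drafting with an obvious meaning. Section 5.5 speaks of patients withdrawn from the study directly beneath its list of reasons for stopping the product. Section 5.5.1, whose title concerns discontinuing the product, calls that event a withdrawal. The sentence in 5.2.1 itself keeps the patient under observation, which does not fit a complete exit. Section 6.7.1, which governs scans specifically, makes no exception by reason for stopping. All of this stands.

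It defeats three stronger readings that a reader might infer:

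- *That the protocol gives no guide to which instruction governs.* There is no formal order of precedence, but 5.5, 6.4.3 and 6.7.1 all point to stopping the drug and continuing to scan.
- *That 5.5.3 proves that these patients leave all assessments.* That section covers withdrawal of consent, not a toxicity stop decided by the investigator.
- *That the response rate would be off by 8.3 points.* That is the weight of any one patient in a cohort of 12, not an estimated effect. An effect needs a literal reading by the site, persistent toxicity, onset at the relevant time and a patient who responds or would have responded.

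The reply does not remove the inconsistency. The QTcF rule shows that the same section can state the narrower instruction. Observation until the toxicity resolves is not a tumour scan, so that clause does not settle the RECIST question.

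**Conclusion.** The general toxicity rule in 5.2.1 is inconsistent with its companion rules, with 5.5 and with 6.7.1. Treatment discontinuation was probably intended, but the literal instruction could cost tumour scans in patients selected by toxicity.

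The consequence is confined to descriptive secondary tumour response data: a missing first scan or an unconfirmed response, each such patient carrying 1/12 of a cohort. This rests on a site reading the rule literally and on the timing assumptions above. The documents give no rate for such toxicity; it is probably low, and none is assumed here. Severity is minor.

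**What to change.** In 5.2.1, replace withdrawal from the study with permanent discontinuation of study treatment, and keep the clause on observing the toxicity until it resolves. Add one sentence: the discontinuation visit, the 28-day follow-up and RECIST assessments under 6.7.1 continue until progression, withdrawal of consent or the final data cut-off, whichever comes first.

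The cut-off limit is needed because the final cut-off in 3.1 and the end of study in 5.6 are defined without reference to progression.

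The cost is one wording change and one sentence. No assessment is added beyond those that 5.5.1, 6.3.8.2 and 6.7.1 already require, and the toxicity threshold and the decision to stop the drug are unchanged.

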5.2.2 Skin reactions

Recommendations for appropriate management of skin reactions, including guidance on doseadjustments for clinically significant and/or intolerable skin reactions that are considered by the investigator to be causally related to AZD9291 will be provided to investigators.

Skin reactions are to be reported as AEs in the eCRF, with additional details captured in the "SKNREAC" eCRF:

- Changes in the characteristics of skin reactions will be collected in the "SKNREAC" eCRF.
- Changes in the CTCAE grade of skin reactions will be collected in the AE eCRF

Photographs of skin reactions may be collected and these photographs should be available for central review by AstraZeneca and for external expert dermatological review if required. Skin biopsies of skin reactions may be taken as per investigator discretion, as per the standard local medical practice. Skin biopsies should ideally be taken in subjects with clinically significant or grade > 3 skin reaction.

5.2.3 Diarrhoea

Recommendations for appropriate management of diarrhoea, including dose-adjustments for adverse events of diarrhoea that are of CTCAE grade \geq 3 or that are clinically significant and/or intolerable and considered by the investigator to be causally related to AZD9291, will be provided to investigators. Changes in CTCAE grade of diarrhoea will be captured in the AE eCRF.

5.2.4 **Duration of therapy**

Patients should continue on treatment with AZD9291 until discontinuation criteria is met. There is no maximum duration of treatment as patients may continue to receive AZD9291 beyond RECIST 1.1 defined progression as long as they are continuing to show clinical benefit, as judged by the investigator.

If AZD9291 is discontinued for any reason, the patient must complete all assessment at discontinuation visit specified in study plan (Table 2).

5.2.5 Treatment compliance and accountability

The investigational product should only be used as directed in this protocol. Details of treatment with investigational product for each patient will be recorded in the Case Record Form.

Patients should return all unused medication and empty containers to the investigator.

The study personnel at the investigational site will account for all drugs dispensed and for appropriate destruction. Certificates of delivery and destruction should be signed.

5.3 Rationale for dose regimen

The dose of 80 mg once daily (with potential dose reduction to 40 mg) was selected for the registration studies outside China. From a review of all available safety, tolerability, PK and efficacy data from study D5160C00001, in patients with advanced NSCLC who have progressed following prior therapy with a prior EGFR-TKI agent. At the Investigator Brochure (IB) data cut-off of 19 November 2013, AZD9291 had been administered across the dose range of 20 to 240 mg once daily in this study: 20 mg (n=21), 40 mg (n=55), 80 mg (n=47), 160 mg (n=40) and 240 mg (n=7). No dose limiting toxicities (DLTs) have been reported at any dose level in the escalation cohorts during the 21-day DLT evaluation period. Patients have once daily doses of AZD9291 for durations of up to at least 10 months depending on the dose level. Emerging efficacy data has demonstrated durable objective responses from the starting dose level of 20 mg once daily (Ranson, WCLC 2013). The selected 80 mg dose is four fold higher than the minimum efficacious dose tested in study D5160C00001, whilst still being one third of the maximum dose level investigated (240 mg). The 80 mg dose level is considered to have a safety and tolerability profile appropriate for chronic administration to patients with advanced NSCLC.

Based on data for study D5160C00001 there is no difference in PK between Western and Asian patients and study D5160C00001 contained a high proportion of patients from Asian countries. Therefore 40 and 80 mg have been chosen as the dose for investigation in this pharmacokinetic study as PK exposure is expected to be similar to that seen in study D5160C00001, is expected to be well tolerated and produce durable objective responses (in T790M positive tumours).

5.4 Benefit/risk and ethical assessment

5.4.1 **Potential benefits**

This study is a PK study with AZD9291, a potent and specific, irreversible dual inhibitor of both the sensitising EGFR mutations and the T790M resistance mutation with more potency towards mutant EGFRs compared to wild-type EGFR. Non-clinical data suggests that dual inhibition can result in anti-proliferative and pro-apoptotic activity in tumour models harbouring one or both of these mutations. Therefore AZD9291 may have the potential to provide clinical benefit both in terms of increased efficacy and decreased epidermal growth factor receptor wild type toxicity in patients with advanced EGFRm+ NSCLC who are either treatment-naïve or who have had disease progression after treatment with an EGFR TKI agent (+/- additional chemotherapy) and are diagnosed with T790M+ NSCLC. In the first line treatment population AZD9291 may have the potential to delay the development of EGFR TKI resistance via the T790M mechanism.

5.4.2 Overall benefit-risk and ethical assessment

In the locally advanced or metastatic NSCLC patients who became refractory to a prior EGFR TKI treatment, their overall survival duration is very low (~16 months for the 2nd line patients. \sim 10 months for third line patients). There is a huge unmet clinical need for novel therapeutic agents for those patients who have developed the resistance mutation. There are no established well proven therapeutic options for this specific T790M+ NSCLC patient population. Although there can be no certainty of clinical benefit to patients, the biological hypothesis and non-clinical data with AZD9291 support the notion that dual EGFR mutation inhibition may be a valid target for the treatment of NSCLC tumours driven via this pathway and may, in addition, delay the development of resistance via T790M in the first line therapy naive population. The selected starting dose for this study is within the range that is predicted to provide biological activity based upon non-clinical explants models, in accordance with the ICH S9 Nonclinical Evaluation for Anticancer Pharmaceuticals Section III.A principle of selecting a dose 'that is expected to have pharmacologic effects'. The toxicological profile of AZD9291 has been evaluated in rats and dogs in studies of up to one month in duration. In accordance with ICH S9 Nonclinical Evaluation for Anticancer Pharmaceuticals which states in Section III.C that 'In Phase 1 clinical trials, treatment can continue according to the patient's response' (ICH S9), dosing of AZD9291 will extend beyond one month if there is some evidence of therapeutic benefit (ie, lack of disease progression with an acceptable tolerability profile). The non-clinical safety profile has not identified any risks that would preclude investigation in this setting. The study design aims to minimise potential risks, and monitoring is in place for those risks deemed to be most likely or serious.

The investigation of AZD9291 in this patient population appears acceptable, based upon the non- clinical safety profile, the lack of effective alternative treatments available to patients, the limited life expectancy due to malignant disease, and the strength of the scientific hypothesis under evaluation. Thus the benefit/risk assessment for this Phase I study support the oral administration of AZD9291 to patients with advanced NSCLC in the post-EGFR TKI treatment failure and treatment-naive settings, according to the proposed study design.

Patients will receive a single dose of AZD9291 as the tablet formulation on Day 1 then after 7 ± 2 days washout, multiple dosing, once daily will be initiated. PK samples will be collected following single dose (Cycle 0) and multiple dose (Cycle 1 Day 8 and Cycle 2 Day 1) to enable characterisation of the AZD9291 phamacokenitics.

The collection of samples to allow investigation of the presence and/or identity of metabolites of AZD9291 and, if appropriate, characterise their pharmacokinetics will generate data to allow AstraZeneca to fulfill regulatory requirements related to the testing of the safety of metabolites.

